6. STUDY DESIGN

a) Type of study

Randomized, double-blind, placebo controlled trial

b) Assessments

Carotid IMT measurements and analysis will be led and coordinated by [name] and [name] at University College, London, UK where there is extensive experience in running large clinical vascular research studies. Data will be

acquired using a standard ultrasound scanning protocol.⁴¹ Both sonographer and participant will be positioned to facilitate high quality, reproducible images. The same ultrasound system and preset image parameter settings (e.g. depth, gain, persistence, dynamic range, post processing) will be used throughout the study. Ultrasound equipment will be calibrated before commencement and every six months subsequently using an ultrasound phantom or as part of each site's local annual service/ calibration.

Right and left carotid arteries will be interrogated in B mode with a 7.0 MHz or higher broadband linear array transducer with concurrent recording of 3-lead ECG. A plaque screen (defined as focal thickening ≥ 1.5 mm or 50% greater than surrounding IMT) of the near and far walls of the common carotid artery (CCA), bulb and internal carotid artery segments will be performed. Then longitudinal images of the common carotid artery will be obtained at anterior, lateral and posterior angles, using Meijer's arc to standardize the transducer angle.

If a participant is found to have asymptomatic high grade carotid stenosis (i.e. $>50\%$) on scanning, cardiovascular risk factor management will be reviewed and arrangements made by their site Principal Investigator (with verbal consent) to facilitate further investigation and treatment as appropriate - usually via the participant's primary care physician. However, our experience, including in older populations with established angiographic coronary disease, suggests that significant stenosis affected $<1\%$ of the study population.⁴² Participants will be eligible to enter and remain in the trial unless cIMT measurements of adequate quality cannot be obtained e.g following carotid artery surgery. Incidental findings, such as tumours or dissection of the carotid artery, will also be reported to the site PI.

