c) Pregnancy: Women of childbearing age will be asked about pregnancy status and contraceptive usage and a urine pregnancy test will be conducted (following informed consent – see below – and prior to entering the Run-In Period). There have been

several recent trials of metformin use in pregnancy, especially for treatment of gestational diabetes mellitus. Systematic review of these trials concludes no adverse effects of metformin as compared with insulin therapy.^{51,52} Nonetheless in this trial we will not recruit those wanting to become pregnant and will discontinue study drug in women who become pregnant. All such pregnancies will be notified to the pharmacovigilance sponsor using the standard pregnancy notification form of the sponsor and the pregnancy followed to outcome.

d) Run-in Period: Those who choose to participate will be invited to give informed consent as per Good Clinical Practice standards and will be invited to enter the three month Run-In Period. They will be given a unique identifying number based on the country of origin, specific site and sequence of recruitment; this will be used for all subsequent correspondence, transfer of samples and data input. They will be encouraged to conduct frequent home blood glucose monitoring (HBGM) and record the results in a standardised Study Diary designed to record (and permit easy extraction) of changes in insulin dosages and episodes of hypoglycaemia (severe or symptomatic). Technique will be reinforced by study nurses. "Sick day rules" as in usual clinical care will be reinforced and supplemented using information printed in the Study Diary.

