responsible for extracting validation information from clinical records. Adherence will be assessed by tablet counts 3-6 monthly (which will be documented on the electronic Case Report Form).

f) Randomisation visit: At the end of the three-month Run-In Period, participants will attend after avoiding strenuous exercise and having fasted from 10 pm the previous evening including avoidance of smoking and caffeine (free water intake permitted). This visit will include: (i) check of adherence to study medication over the third month (tablet counts); (ii) measurement of the primary endpoint (carotid IMT); and (iii) repeat anthropometric and metabolic assessments (see Schedule of Assessments – Section 2). Pregnancy testing will be conducted if indicated.

Participants with: (i) less than 70% adherence on tablet counts who are non-adherent in the view of site staff; or (ii) inadequate quality carotid images in the view of the local sonographer will be withdrawn at this stage i.e. before randomization. Those who met HbA1c criteria at the screening visit (R1) but who now have HbA1c < 7.0% (53 mmol/mol) will not be excluded at this visit.

Participants remaining eligible, who satisfy the study inclusion/ exclusion criteria and have provided written informed consent can then be randomized to metformin or placebo by telephone via a call to the study Interactive Voice Response System (IVRS) or electronically via the study portal for the study electronic CRF, see section 14.1.

g) Follow up: see Schedule of Assessments (page 10) and Section 10 (page 31). Participants will then have visits at one month, three months and 3-6 monthly thereafter until study cessation. As almost all patients will be attending for routine clinic care, we envisage that most visits will be conducted by study nurses in the same location and time as usual care and include:

- assessment of adherence
- capture of data on prespecified clinical events (see Section 13)
- safety questionnaire
- Diabetes Treatment Satisfaction Questionnaire
- routine clinic bloods and additional trial specific bloods
- capture of data on prespecified concurrent medications
- capture of data held in Study Diary to be used by patient to record hypoglycaemic episodes and insulin dose

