Following an episode of severe hypoglycaemia, standard causes of hypoglycaemia will be reviewed in order to identify an obvious precipitating factor (insulin dosing error, accidental intravascular injection or other injection site problem, excessive unplanned exercise, missed meal, alcohol consumption, renal impairment, loss of warning signs). HbA1c will be repeated where the most recent available value is more than six weeks previously. Where no obvious reversible precipitant is identified, participants will be advised to reduce insulin dose by 10% over the following month and perform more intensive HBGM. At review, after one month, the aim will be to uptitrate insulin dose once again, *unless* glycaemic target HbA1c < 7.0%/ 53 mmol/mol continues to be met on the reduced dose *or* there have been further episodes of major or unacceptable minor hypoglycaemia.

If the participant has a major hypoglycaemic event and is brought into the Emergency Department, this will only be considered an SAE if the hospital stay is longer than 12 hours. Minor hypoglycaemic episodes (i.e those not requiring assistance from another individual) will not be recorded as an AE.

j) Participant discontinuation: Participants will be free to discontinue study medication at any point during the study. Where possible, follow up in the trial will be continued with continuing titration of insulin doses to target. If informed consent for follow-up is withdrawn, data collected up to self-withdrawal will be included in the study unless the participant wishes otherwise. Clinical samples will be destroyed at their request.

k) Source documents: Participants will be asked to provide informed consent for investigators to obtain copies of official documentation (discharge letter or clinic letter) of any cardiovascular events which will be made available at the request of study monitors. This will also apply for Severe Adverse Event reporting (Section 13, page 34 for which we will obtain copies of official documentation (discharge letter or clinic letter).

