In these cases, treatment will be restarted where possible in accordance with the Investigator's clinical judgement, local practice, standard-of-care, and national guidelines (renewed titration from a lower starting dose is not usually required unless interruption has been prolonged e.g. more than four weeks). Where treatment interruption has persisted for four weeks or more it will be documented as permanent.

Withdrawal of treatment: Investigators will withdraw from treatment any participant who develops any of the following:

- Pregnancy: discontinue if participant becomes, or intends to become, pregnant
- Development of new contraindications to metformin
 - o hepatic impairment (ALT > 3.0 ULN)
 - o renal impairment with eGFR <30 mL/min/1.73m² during study – see page 28
- Biochemically-confirmed severe lactic acidosis (>5.0 mmol/L with acidosis)
- Hypersensitivity to metformin

Dose reduction of treatment: Where eGFR falls below 45 ml/min/ 1.73m² on any measurement Investigators should permanently reduce metformin dose to 500 mg twice daily.

Withdrawal from study: Investigators will withdraw from the study any randomized participants with:

[figure not shown]
- confirmed pregnancy
- withdrawal of consent for follow-up
- any other reason agreed between the participant and the site Principal Investigator

At the end of the study: No further study medication will be provided.

Assessment of adherence: Tablet counts will be carried out by study nurses following at relevant study visits, including the final clinic visit, to assess adherence. This will be documented in the eCRF. Site medical and nursing staff will also discuss and reinforce adherence to study medication with participants.

Concomitant medication. No concomitant medication is specifically excluded.

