All Serious Adverse Events must be assessed for seriousness, causality, severity (which will be undertaken by Principal Investigators at each site) and expectedness (which is the responsibility of the Chief Investigator).

Severity. This should be assessed and described using the following categories:

Mild	awareness of event but easily tolerated
Moderate	discomfort enough to cause some interference with usual activity
Severe	inability to carry out usual activity.

All SAEs arising during the clinical trial will be reported by entering the details into the eCRF as soon as reasonably practicable and in any event within 24 hours of first becoming aware of the event. Any follow up information should also be reported.

Serious adverse events recorded in the eCRF will be transferred to the Glasgow Pharmacovigilance database.

SAEs that occur at any time after the inclusion of the subject in the study (defined as the time when the participant signs the informed consent) up to 30 days after the subject completed or discontinued the study will be reported.

The participant is considered to have completed the study after the completion of the last visit when any remaining medication will be collected. The date of discontinuation is when a subject and/or investigator determines that the subject can no longer comply with the requirements for any further study visits or evaluations.

All **SUSARS** will be reported in an expedited fashion to the MHRA and other relevant regulatory authorities as well as to the relevant IRBs and Ethics Committees.

Fatal or life threatening SUSARs. Not later than 7 days after the CI had information that the case fulfilled the criteria for a fatal or life threatening SUSAR, and any follow up information within a further 8 days.

All other SUSARs. Not later than 15 days after the CI had information that the case fulfilled the criteria for a SUSAR. The Glasgow Clinical Trials Unit Pharmacovigilance (PV) Office will report SUSARs on behalf of the CI to the MHRA and other relevant regulatory authorities via the eSUSAR reporting system and to the Ethics committee in paper format.

A copy of the SUSAR report will be forwarded by the PV Office to the sponsor's representative in other host countries for submission as appropriate to the national ethical and regulatory authorities.

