2. ANALYSIS

2.1. STUDY POPULATIONS AND ANALYSIS SETS

The Screened population will consist of all subjects screened for inclusion into the study.

The Intention To Treat (ITT) population will consist of all subjects randomised, regardless of subsequent participation in the study.

The modified-ITT (mITT) analysis set will include all subjects from the ITT population with data as available (without imputation) for analysis for each individual outcome.

The Per Protocol (PP) population will consist of all members of the ITT population with no major protocol deviations (met inclusion and exclusion criteria and no prohibited medications at randomisation), and who have cIMT available at treatment visits 1, 8, 12 and 16. All identified protocol deviations will be reviewed prior to unblinding the dataset, and classified as major or minor.

The Safety population will consist of all members of the ITT population who received at least one dose of study medication.

For any analyses to be carried out in multiple populations, if the populations are identical (e.g. if all members of the ITT population take at least one dose of study medication, then the ITT and Safety population are the same), then the analysis will only be reported once.

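### Protocol Section 6(b) makes adequate carotid images a condition for staying in the trial after randomisation, so a disease-related event can end collection of outcomes that need no carotid image

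*Protocol*

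**What the plan says.** **Images.** Protocol Section 6(b), after describing incidental carotid stenosis, says that participants will be "eligible to enter and remain in the trial unless cIMT measurements of adequate quality cannot be obtained e.g following carotid artery surgery". Section 7.2(xii) already excludes people with previous carotid surgery or inadequate images. Section 7.3(f) adds that, at the randomisation visit, participants with "inadequate quality carotid images in the view of the local sonographer will be withdrawn at this stage i.e. before randomization".

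**Stopping study drug.** Section 7.3(j) addresses participants who stop study medication: "Where possible, follow up in the trial will be continued with continuing titration of insulin doses to target".

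**Leaving the study.** Section 8 has a list headed "Investigators will withdraw from the study any randomized participants with". It includes confirmed pregnancy, withdrawal of consent for follow-up, and "any other reason agreed between the participant and the site Principal Investigator". Pregnancy also appears in Section 8 under withdrawal of treatment. Section 7.3(c) says that the trial "will discontinue study drug in women who become pregnant" and follows the pregnancy to outcome; Section 13 repeats the follow-up to outcome.

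**What continues after exit.** Section 7.3(j) keeps data collected up to self-withdrawal unless the participant objects. Section 13 says that serious adverse events occurring after consent and "up to 30 days after the subject completed or discontinued the study will be reported". Sections 6(b) and 7.3(l) provide for consented linkage to national records where permitted.

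**Analysis.** SAP 2.1 defines the ITT population as "all subjects randomised, regardless of subsequent participation in the study", but analyses each outcome on available data. SAP 2.4.1 averages whatever angles and sides are available at each time point.

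**The concern.** A trial that compares arms as randomised should keep collecting data on everyone randomised unless they withdraw consent. Section 6(b) instead ties staying in the trial to whether one endpoint can still be measured. Its own example, carotid surgery, is a treatment for the disease that the primary endpoint tracks, and carotid endarterectomy is itself an adverse event of medical interest in Section 13. The loss could therefore be related to outcome.

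Most of what would be lost has nothing to do with carotid ultrasound. The interpretation rule for the secondary endpoints (significant improvement in two or more) depends on those data. Retinopathy is the most exposed, because photographs are taken only at 0 and 36 months: anyone who leaves in between has no observed retinopathy outcome. Section 6(d) already concedes that this endpoint, with 400 participants photographed, needs a hazard ratio of 0.40 for 80% power.

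The ITT definition keeps such people in the denominator but does not recover their data. Sites reading Section 6(b) and sites reading Sections 7.3(f) and 7.3(j) could also treat the same participant differently.

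**Working it through.** **1. Does the condition reach beyond entry?** Sections 7.2(xii) and 7.3(f) already deal with carotid surgery and poor images before randomisation. If Section 6(b) were only about entry, its reference to remaining would add nothing. Its plain effect is therefore after randomisation.

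**2. What a participant would lose.** Take a one-sided endarterectomy at month 14, after the month 12 scan.

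| Item | If Section 6(b) ends participation | If follow-up continues |
|---|---|---|
| cIMT at 0 and 12 months | kept; person stays in the primary model | kept |
| cIMT at 24 and 36 months | lost | other side usable under SAP 2.4.1 |
| LDL cholesterol at 24 and 36 months | lost | collected |
| HbA1c, eGFR and weight after month 14 | lost | collected |
| Insulin dose and hypoglycaemia after month 14 | lost | collected |
| Retinopathy at 36 months | lost | collected |
| Serious adverse events | reported to 30 days after exit | collected throughout |
| Other adverse events of medical interest (eye, foot, renal) | lost after exit | collected throughout |

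**3. How many people?** The only relevant frequency in the documents is significant stenosis in under 1% (Section 6(b)).
- Planned size: 0.01 × 500 = 5, so fewer than 5.
- Randomised total from Appendix 6: 379 + 50 = 429, and 0.01 × 429 = 4.3, again fewer than 5.

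Stenosis is not surgery, so this is not a count of operations. No rate is given for images that become inadequate for other reasons. If it were 1% to 5% (assumption), that would be about 4 to 21 of 429.

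**4. Effect on power.** Inputs from Section 6(d): difference 0.0167 mm, SD 0.05 mm, 200 per arm, 5% level (two-sided assumed), 90% power.

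Power = Φ[(δ/σ)·√(n/2) − 1.96]. With δ/σ = 0.0167/0.05 = 0.334 and n = 200: Φ(3.34 − 1.96) = Φ(1.38) = 91.6%. The stated 90% reproduces; the required number is 189 per arm, so 200 is rounded up.

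| Extra loss, as % of 500 | Power on top of 20% dropout | Power on top of 25% dropout |
|---|---|---|
| 0% | 91.6% | 89.9% |
| 1% (5 people) | 91.3% | 89.5% |
| 2% (10 people) | 91.0% | 89.1% |
| 5% (25 people) | 89.9% | 87.8% |

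A 1% extra loss costs 0.3 to 0.4 percentage points.

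**5. Possible bias in the primary result (illustration; f and k are assumptions).** If an extra fraction f of one arm were removed entirely, and those people progressed k SD faster than the rest, the difference would shift by about f × k × 0.05 mm.
- f = 0.5%, k = 1: 0.00025 mm, 1.5% of the 0.0167 mm target.
- f = 1%, k = 2: 0.001 mm, 6%.
- f = 2%, k = 3: 0.003 mm, 18%.

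An imbalance of 1% of a 250-person arm is 2.5 people, so an overall total below 5 leaves little room for the larger values. The formula also assumes complete deletion, whereas anyone with a baseline and one follow-up scan stays in the model.

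**The case against.** The sentence in Section 6(b) follows text on incidental stenosis and mainly reassures sites that such participants may stay. The working withdrawal rules are in Sections 7.3(f) and 8, and no passage says outright that visits stop when later images are inadequate. This is fair as to intent, but the wording still reaches people already randomised, and nothing in the protocol overrides it.

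Three stronger readings are tempting and are not supported:

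- *All outcome and safety follow-up is lost.* It is not. Data up to self-withdrawal are kept, serious adverse events are reported for 30 days after exit, pregnancies are followed to outcome, and consented linkage may capture deaths and cardiovascular events. What would go is later visit-based data.
- *The fastest progressors are removed from the primary analysis.* cIMT is read in the distal 1 cm of the common carotid, and the main analysis uses only values below 1.5 mm. Nothing shows that people who need surgery are the extreme progressors on that measure, and those with a follow-up scan stay in the model.
- *Section 8 contradicts Section 6(b) by omitting image failure.* A figure is missing from the available text at the head of the Section 8 list, so no weight can be put on the omission.

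The SAP also offers partial protection. SAP 2.2 reports withdrawals with reasons and timing by arm. SAP 2.4.3 would impute cIMT missing for image reasons, with a similar approach for retinopathy and endothelial function. That imputation relies on baseline covariates, so it would not use the fact of surgery, and it does not replace data that could have been observed.

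On pregnancy, the passages may be cumulative rather than contradictory, and an agreed reason does require the participant's agreement. What stands is that neither says whether data collection continues.

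**Conclusion.** The point holds as a defect of wording with a real but probably small consequence. Section 6(b), followed literally, ends later visits because one endpoint cannot be measured, and carotid surgery makes that reason potentially related to the disease under study. It does not fit with Section 7.3(f), which confines the image rule to the time before randomisation, or with the continued follow-up intended in Section 7.3(j).

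On the documents' own figure, stenosis affects fewer than 5 of 500 people, and a 1% loss costs under half a percentage point of power. Any bias in the primary result cannot be estimated from the documents; the illustrated range rests on assumed selection and assumed imbalance between arms. The firmer cost is avoidable loss of secondary and adverse-event data in randomised participants. If images fail more often than stenosis suggests, that cost grows in proportion.

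**What to change.** 1. In Protocol Section 6(b), remove the reference to remaining in the trial, so that image adequacy is a condition of entry only.
2. State there that inadequate images after randomisation give a missing cIMT value, or a one-sided value where the other side is readable, and that all other outcome and safety follow-up continues unless consent is withdrawn. The averaging rule in SAP 2.4.1 already accommodates this.
3. Reconcile Sections 7.3(c), 8 and 13 on pregnancy, and Sections 7.3(j) and 8 on other agreed reasons, so that each says whether stopping study drug also ends data collection. How these participants are managed is for the sponsor and investigators to decide; the request is only that the passages agree.

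The cost is a short protocol amendment and a few more routine visits for people who might otherwise have left.

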We intend to analyse IMT data using repeated measures regression analysis assuming a linear progression in IMT measurements. We expect a mean progression of 0.044mm over 3 years (in the control arm) and a standard deviation (SD) for progression of 0.05 mm; therefore a final sample size of 200 per treatment arm will provide 90% power (at 5% significance level) to detect a difference of at least one third of an SD (0.0167mm) in 3 year progression of averaged mean cIMT between treatment arms - an effect size more conservative than reported for acarbose, statins, and TZDs on cIMT.

We therefore aim to recruit 500 patients (allowing for around 20-25% treatment discontinuation/ drop-out) and making the very conservative assumption that all those discontinuing treatment/ and withdrawing consent would not even have one follow up measurement (in reality this may occur after one or more follow up cIMT measurements so power will be more than this estimate).

Rates of progression and variation of common carotid artery IMT vary widely between different studies and data from T1DM patients, other than the patients in DCCT/EDIC who are younger than this trial participants, are sparse. Our estimate of progression rate over three years (0.044 mm) is at the lower boundary of that reported by Bots in a meta-analysis of cIMT progression rates of control groups (almost all non-diabetic) from published RCTs.⁵⁰ In that analysis the annual rate of change in mean cIMT was 0.0176 mm (95% CI, 0.0149 to 0.0203). Whilst many of the control group participants in this pooled analysis were not on statins (in contrast to many REMOVAL participants with T1DM) almost all were non-diabetic so that their progression rate would be expected to be lower than in diabetes.

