1.4. SAMPLE SIZE AND POWER

Assuming a mean linear progression of 0.044mm over three years (in the control arm) and a standard deviation (SD) for progression of 0.05mm and to have 90% power at a 5% significance level to detect a difference of at least one third of a SD (0.0167 MM) in three year progression of averaged mean far wall cIMT between treatment arms we will require 200 subjects per treatment group. Allowing for 20-25% drop-outs/discontinuations, 500 subjects, in total, will be recruited.

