1.6.2. GENERAL PRINCIPLES

All study data will be summarised as a whole and by treatment group at each study assessment point. Continuous variables will be summarised by the number of observations, number of missing values, mean, standard deviation (SD), median, quartiles and range. Categorical variables will be summarised by the number of observations, number of missing values and the number and percentage of individuals in each category.

Baseline data will be extracted from the Treatment Visit 1 electronic case report form (eCRF) page where possible; if values are missing, then data from the first screening visit (Run-in Visit 1) will be used.

The primary analysis, and all secondary analyses, will be carried out using all randomised individuals who provide sufficient data to conduct the particular analysis, regardless of their adherence to study protocol. For the primary outcome, a sensitivity analysis will be carried out using a Per-Protocol dataset, consisting of those individuals that completed the study according to protocol.

Graphical presentations will be specified and provided according to the results of the final analysis.

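### Participants who stop study drug early but stay in follow-up dilute the slope difference, so the protocol's statement that power will exceed its estimate is not generally true

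*Protocol*

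**What the plan says.** Protocol section 6(d) sizes the trial on the primary endpoint: "a final sample size of 200 per treatment arm will provide 90% power (at 5% significance level"), for a "difference of at least one third of an SD (0.0167mm) in 3 year progression of averaged mean cIMT", with "a standard deviation (SD) for progression of 0.05 mm". SAP section 1.4 repeats the calculation ("we will require 200 subjects per treatment group") and the allowance: "Allowing for 20-25% drop-outs/discontinuations, 500 subjects, in total, will be recruited".

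The protocol's allowance pools two groups, those who discontinue treatment and those who withdraw consent. It assumes that nobody in either group has a single follow-up scan, describes that as very conservative, and says that "in reality this may occur after one or more follow up cIMT measurements so power will be more than this estimate".

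Three other provisions bear on this.
- Protocol section 7.3(j), on participants who discontinue study medication: "Where possible, follow up in the trial will be continued with continuing titration of insulin doses to target".
- Protocol section 6(d) includes everyone with a baseline and at least one follow-up cIMT. SAP section 1.6.2 analyses all randomised participants with sufficient data, "regardless of their adherence to study protocol".
- SAP section 2.4.1 takes the treatment effect from a random-slopes model with a time-by-treatment interaction.

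Neither document reduces 0.0167 mm for participants analysed in the metformin arm after stopping metformin.

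**The concern.** The protocol treats non-measurement as the worst that can happen to someone in the 20-25%. For a person who leaves, it is: any on-treatment scan obtained before leaving adds information. For a person who stops metformin and is still scanned, two things happen. The scans add precision, and the off-treatment part of the slope pulls the metformin arm's mean towards placebo. If stopping is early enough, the second outweighs the first, and the trial has less power than if that person had never been scanned.

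What is at stake is how a null primary result would be read. A reader would set it against a power of at least 90%, whereas the planned as-randomised analysis could have less. The better sites are at keeping early stoppers in follow-up, as section 7.3(j) asks, the less the statement holds.

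**Working it through.** **Inputs from the documents.** Difference 0.0167 mm and SD 0.05 mm for three-year progression; 200 evaluable per arm; 500 recruited, so 250 per arm; allowance q = 20-25%; scans at 0, 1, 2 and 3 years. A two-sided 5% test is used; the documents do not state sidedness.

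**Assumptions, not in the documents.** 0.0167 mm is the difference under full adherence. No further effect accrues after stopping. Stopping placebo causes no dilution. The SD is unchanged. Timing of stopping, and the split between stopping and leaving, are varied.

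**Formula.** Power = Φ(d / (0.05 × √(2/n)) − 1.96), with n per arm.

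**Step 1: the plan's own figure.** With n = 200 the standard error is 0.05 × √(2/200) = 0.0050. Then 0.0167/0.0050 = 3.34 and Φ(1.38) = 91.6%. The stated 90% reproduces, with slight rounding up. Also 400/0.80 = 500.

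**Step 2: the plan's no-follow-up case with 500 recruited.** At 20% unmeasured, n = 200 and power is 91.6%. At 25%, n = 187.5 and power is 89.9%.

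**Step 3: stoppers followed and analysed as randomised.** Now n = 250 and the standard error is 0.05 × √(2/250) = 0.00447. With no dilution, power is 96.2%. With dilution, d = 0.0167 × (1 − q(1 − k)), where k is the share of the effect that a stopper's fitted slope keeps. For stopping at time s, k is the least-squares slope of min(t, s) on t = 0, 1, 2, 3, with weights −0.3, −0.1, 0.1, 0.3. For s = 1 year, for example, k = −0.1 + 0.1 + 0.3 = 0.30.

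| When all of the 20% / 25% stop | k | Power, q = 20% | Power, q = 25% |
|---|---|---|---|
| At once | 0 | 84.8% | 80.0% |
| At exactly 3 months | 0.075 | 86.1% | 81.9% |
| At 1 year | 0.30 | 89.5% | 86.9% |
| Evenly over 3 years | 0.50 | 91.9% | 90.4% |
| Evenly over years 1 to 3 | 0.675 | 93.7% | 92.9% |

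First row in full: 0.0167 × 0.80 = 0.01336, 0.01336/0.00447 = 2.99, Φ(1.03) = 84.8%; and 0.0167 × 0.75 = 0.01253, 0.01253/0.00447 = 2.80, Φ(0.84) = 80.0%.

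**Step 4: a mix.** Half of q are unmeasured, and half stop at once and are followed. At 20%, n = 225, the diluting share is 0.10/0.90 = 0.111, d = 0.01484 and power is 88.3%. At 25%, n = 218.75, the share is 0.125/0.875 = 0.143, d = 0.01431 and power is 84.9%.

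**Step 5: break-even.** At 250 per arm, 90% power needs d = (1.96 + 1.28) × 0.00447 = 0.0145, so dilution of up to about 13% is tolerable. A followed stopper costs more power than an unmeasured one when the share of effect lost exceeds (1 − √0.80)/0.20 = 0.53 at 20%, or (1 − √0.75)/0.25 = 0.54 at 25%.

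**Sensitivity to the model.** SAP section 2.4.1 lists baseline cIMT as a predictor. If only years 1 to 3 then serve as outcomes, a stop at any time up to 1 year loses the whole slope effect (84.8% / 80.0%), and even stopping over three years gives 89.9% / 87.5%.

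**The case against.** The strongest reply is that the sentence describes stopping or leaving after one or more follow-up scans, that is, after about a year. For stopping spread over years 1 to 3 the calculation supports it: 93.7% / 92.9% against 91.6% / 89.9% in the unmeasured case. This stands. The protocol does not say that follow-up can only raise power, and it should not be read that way. What it leaves out is the participant who stops before or near the first scan and is followed. It still calls the no-scan assumption very conservative for the whole pooled group.

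A reader might infer from the documents that most stopping will be early. They do not show this. The Visit 5 text in protocol section 10 concerns people who tolerate only a reduced dose, not people who stop. Section 8 does list gastrointestinal effects as very common, but says that they usually resolve and are lessened by titration. No timing is given anywhere.

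A reader might also infer that the trial is underpowered. That needs 0.0167 mm to be a full-adherence effect. Both documents call it a difference between treatment arms and say no more. If it is already the as-randomised difference, no dilution applies and 250 per arm fully measured gives 96.2%. The 80-85% figures are moreover a corner case: everyone in the allowance stops at once, nobody leaves, and all are scanned. With half lost and half stopping evenly over three years, power is 91.7% / 90.0%.

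Finally, no number in the plan is miscalculated, and the sentence drives no analysis or decision rule. The uncertainty that the protocol admits in cIMT variation matters as much: an SD of 0.055 mm alone gives 85.9% at 200 per arm. That limits the weight of the point but does not make the sentence correct.

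**Conclusion.** The point holds in limited form. The statement that power will exceed the estimate is true for people who leave after on-treatment scans and for people who stop late. It is not true for people who stop early and are followed and analysed as randomised, as both documents intend. Under the assumptions listed in the working, power with 500 randomised runs from about 80% (25% stopping at once) to about 92% (20% stopping evenly over three years), and is higher for later stopping. Half lost and half stopping at once gives 88% / 85%. This is an unsupported assurance about power. It is neither an arithmetic error nor evidence that actual power is below 90%.

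**What to change.** In protocol section 6(d), delete the description of the no-scan assumption as very conservative. Also delete the closing clause that power will exceed the estimate, or limit that clause to people who leave after on-treatment scans or who stop late.

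In protocol section 6(d) and SAP section 1.4, state whether 0.0167 mm is the difference averaged over all randomised participants or the difference under full adherence. If it is the latter, give power as a range by timing of stopping, with its assumptions. Possible wording: *If 20-25% of participants stop study drug, all are followed and no effect accrues after stopping, power with 500 randomised is about 80-85% for stopping at once, 87-89% at one year and 90-92% for stopping spread evenly over three years.*

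Recompute these figures for the number actually randomised. Protocol Appendix 6 lists 379 + 50 = 429. If that is the full number (214.5 per arm), the stopping-at-once case becomes about 79% / 74%.

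The cost is a few sentences and a less favourable stated figure. Enrolment, conduct and the analysis are unchanged.
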